### **11.3.2.2 Urine Parameters**

Urine samples will be collected from a morning spot. The tests will be performed at the Investigator's site (pregnancy test, drug screen). The subjects should empty their bladder (and discharge the urine) around 6 am, drink approximately 1 glass of water, and wait approximately 2 h before the urine samplings.

Urine drug screen will detect amphetamines, barbiturates, cannabinoids, cocaine metabolites, opiates, and phencyclidine.

## **12. VISITS**

### **12.1 Schedule**

This is an outpatient study (see Section 2 **Study Flow Chart**). The assessments of Visit 1 (Screening Visit) can be done over several days within the screening period. Visit 13

---

should occur 2 days after Visit 12. The other visits can take place within  $\pm$  2 days (up to Visit 9) and  $\pm$  3 days (after Visit 9) of the schedule.

Visit 13 should be avoided during the extended holiday period of December/January (the last week of December and the first 2 weeks of January). To reach this objective, Visit 2 should not be scheduled during the last 3 weeks of July.

## **12.2 Assessments**

The following procedures will be performed (see Section 11 **Study Endpoints**):

### **12.2.1 Visit 1 (Screening Visit; Day -21 to -1)**

- Informed consent (women of childbearing potential are requested to use a medically approved contraceptive method during the entire study)
- Demographic characteristics (gender, age, ethnic origin)
- Menopausal status (and estrogen replacement therapy status)
- Smoking status
- Medical history
- Physical examination
- Height
- Weight
- Waist circumference
- Vital signs (supine and standing blood pressure and heart rate)
- ECG
- Binge eating disorder (QEWP-R)
- Dietary interview (calculation of the energy requirement)
- Serum pregnancy test (women of childbearing potential only)
- TSH
- Urine drug screen (test performed at the Investigator's site)
- HbA1c
- Hematology
- Blood chemistry
- Previous (within 1 month) and concomitant medication records
- AEs and SAEs records

### **12.2.2 Visit 2 (Baseline Visit; Day 0)**

- Physical examination
- Weight
- Waist circumference
- Vital signs (supine and standing blood pressure and heart rate)
- Dietary interview (dietary prescription)
- Food intake
- Food habits

---

- IWQOL
- Serum amylase (blood can be collected at any of the Visits 2, 3, 4, 5, 9, or 13)
- Genomic tests (blood can be collected at any of the Visits 2, 3, 4, 5, 9, or 13) (tests not mandatory)
- Serum pregnancy test (women of childbearing potential only)
- Urine pregnancy test (women of childbearing potential only) (test performed at the Investigator's site)
- Serum insulin
- HbA1c
- Serum CRP
- Hematology
- Blood chemistry
- Vitamins
- Concomitant medication record
- Randomization
- Dispensation of study product (administration begins the following day)
- AEs and SAEs records

#### **12.2.3 Visit 3 (First Double-Blind Visit; Day 8 ± 2)**

- Weight
- Waist circumference
- Vital signs (supine and standing blood pressure and heart rate)
- Dietary interview (dietary check)
- Plasma glucose
- Serum insulin
- Concomitant medication record
- Investigational product accountability
- Dispensation of study product
- AEs and SAEs records

#### **12.2.4 Visit 4 (Second Double-Blind Visit; Day 15 ± 2)**

- Weight
- Waist circumference
- Vital signs (supine and standing blood pressure and heart rate)
- Dietary interview (dietary check)
- Plasma glucose
- Serum insulin
- Serum albumin
- Concomitant medication record
- Investigational product accountability
- Dispensation of study product

---

- AEs and SAEs records

#### **12.2.5 Visit 5 (Third Double-Blind Visit; Day 29 ± 2)**

- Weight
- Waist circumference
- Vital signs (supine and standing blood pressure and heart rate)
- Dietary interview (dietary check)
- Food intake
- Plasma glucose
- Serum insulin
- Serum albumin
- Concomitant medication record
- Investigational product accountability
- Dispensation of study product
- AEs and SAEs records

#### **12.2.6 Visit 6 (Fourth Double-Blind Visit; Day 43 ± 2)**

- Weight
- Waist circumference
- Vital signs (supine and standing blood pressure and heart rate)
- Dietary interview (dietary check)
- Concomitant medication record
- Investigational product accountability
- Dispensation of study product
- AEs and SAEs records

#### **12.2.7 Visit 7 (Fifth Double-Blind Visit; Day 57 ± 2)**

- Weight
- Waist circumference
- Vital signs (supine and standing blood pressure and heart rate)
- Dietary interview (dietary check)
- Food intake
- Concomitant medication record
- Investigational product accountability
- Dispensation of study product
- AEs and SAEs records

#### **12.2.8 Visit 8 (Sixth Double-Blind Visit; Day 71 ± 2)**

- Weight

---

- Waist circumference
- Vital signs (supine and standing blood pressure and heart rate)
- Dietary interview (dietary check)
- Concomitant medication record
- Investigational product accountability
- Dispensation of study product
- AEs and SAEs records

#### **12.2.9 Visit 9 (Seventh Double-Blind Visit; Day 85 ± 2)**

- Physical examination
- Weight
- Waist circumference
- Vital signs (supine and standing blood pressure and heart rate)
- Dietary interview (dietary check)
- Food intake
- Serum pregnancy test (women of childbearing potential only)
- Serum insulin
- TSH (subjects on replacement therapy with thyroid hormones or preparations only)
- HbA1c
- Serum CRP
- Hematology
- Blood chemistry
- Vitamins
- Concomitant medication record
- Investigational product accountability
- Dispensation of study product
- AEs and SAEs records
- Reinforcement of study-related instructions

#### **12.2.10 Visit 10 (Eighth Double-Blind Visit; Day 113 ± 3)**

- Weight
- Waist circumference
- Vital signs (supine and standing blood pressure and heart rate)
- Dietary interview (dietary check)
- Food intake
- Concomitant medication record
- Investigational product accountability
- Dispensation of study product
- AEs and SAEs records

---

### **12.2.11 Visit 11 (Ninth Double-Blind Visit; Day 141 ± 3)**

- Weight
- Waist circumference
- Vital signs (supine and standing blood pressure and heart rate)
- Dietary interview (dietary check)
- Food intake
- Concomitant medication record
- Investigational product accountability
- Dispensation of study product
- AEs and SAEs records

### **12.2.12 Visit 12 (Tenth Double-Blind Visit; Day 169 ± 3)**

- Weight
- Waist circumference
- Vital signs (supine and standing blood pressure and heart rate)
- Dietary interview (dietary check)
- Food intake
- Food habits and satisfaction
- Concomitant medication record
- Investigational product accountability
- AEs and SAEs records

### **12.2.13 Visit 13 (First Follow-up Visit; Day 171; 2 days after Visit 12) (Last visit if entering extension study)**

- New informed consent (subjects entering extension study)
- Physical examination
- Weight
- Waist circumference
- Vital signs (supine and standing blood pressure and heart rate)
- Dietary interview (dietary check)
- IWQOL
- Serum pregnancy test (women of childbearing potential only)
- Serum insulin
- HbA1c
- Serum CRP
- Hematology
- Blood chemistry
- Vitamins
- Concomitant medication record
- AEs and SAEs records

---

### **12.2.14 Visit 14 (Second Follow-up Visit; Day 197 ± 3)**

- Weight
- Waist circumference
- Vital signs (supine and standing blood pressure and heart rate)
- Dietary interview (dietary check)
- Concomitant medication record
- AEs and SAEs records

## **12.3 Definition of Source Data**

The list of information considered as source data that must be shown in the subject's chart is provided in Appendix 5.

# **13. SAFETY MONITORING AND REPORTING**

## **13.1 Adverse Event and Device Deficiency**

### **13.1.1 Investigational Product in this Clinical Study**

In this clinical study, the investigational product, Gelesis100, is considered as a medical device. Therefore, all safety monitoring and reporting procedures are governed by medical device guidelines and regulations.

### **13.1.2 Definitions**

An AE is any untoward medical occurrence (sign, symptom, illness, abnormal laboratory value, or other medical event) in a subject, whether or not related to the investigational medical device. This includes events related to the procedures involved (any procedure in the Clinical Investigation Plan).

A SAE is any AE that:

- led to death
- resulted-in a life-threatening condition
- resulted-in a permanent impairment of a body structure or a body function
- required inpatient hospitalization or prolongation of existing hospitalization for  $\geq 24$  h (elective hospitalizations and/or hospitalizations for treatment of pre-existing conditions that did not worsen from baseline are not considered AEs and should not be reported as SAEs)
- resulted-in a medical or surgical intervention to prevent permanent impairment to a body structure or a body function
- led to fetal distress, fetal death or a congenital abnormality, or birth defect

A device deficiency is an inadequacy of the medical device with respect to its identity, quality, durability, and safety (e.g., use errors and inadequate labeling). Medical device

---

deficiency can lead to an adverse device effect (ADE) or a serious ADE (SADE) (see below).

For the purpose of this study and for reporting purposes, all device deficiencies that could have led to SAEs, if suitable action had not been taken or intervention had not been made, or if circumstances had been less fortunate, will also be considered as SAE.

An ADE is an AE with a reasonable causal relationship to the use of the investigational medical device (i.e., an AE assessed as either “most probably related” or “possibly related” to the use of medical device) (see Section 13.1.3).

An unanticipated ADE (UADE) is an ADE not previously reported or an ADE that occurs with specificity, severity, frequency, or outcome that is not consistent with the current Investigator’s Brochure (8).

A SADE is a SAE with a reasonable causal relationship to the use of the investigational medical device (i.e., a SAE assessed as either “most probably related” or “possibly related” to the use of medical device). For Canada, this definition is equivalent to the Canadian definition of an incident.

An unanticipated SADE (USADE) is a SADE not previously reported or an SADE that occurs with specificity, severity, frequency, or outcome that is not consistent with the current Investigator’s Brochure. In US, this definition is equivalent to the definition of an UADE in Medical Device Reporting regulation at Title 21.

### **13.1.3 Adverse Event and Device Deficiency Recording, Assessment, and Reporting Procedure**

All AEs regardless of seriousness or relationship to the investigational medical device including those occurring during the screening period (after the signature of the Informed Consent Form) are to be recorded in the appropriate electronic CRF.

AEs reported by subject will be discussed in details and recorded by the Investigator at each visit. AEs will be collected until 28 days after the last administration of the investigational medical device (i.e., until subject terminates his/her participation in the study).

The Investigator should specify the date of onset, severity, action taken with respect to the investigational medical device, corrective treatment, outcome, and whether or not there is a reasonable possibility that the AE may have been caused by the use of the investigational medical device.

AEs are graded as follows:

- Mild: sign or symptom, usually transient, requiring no special treatment and generally not interfering with usual activities.

---

- Moderate: sign or symptom, which may be ameliorated by simple therapeutic measures, may interfere with usual activity.
- Severe: sign or symptom intense or debilitating and interfering with usual activities without being immediately life-threatening. Recovery is usually aided by therapeutic measures.
- Very severe: sign or symptom life-threatening. Urgent intervention indicated.

The assessment of the relationship of an AE to the use of the medical device is a clinical decision based on all available information at the time of the completion of the electronic CRF:

- Most probably related: follows a reasonable temporal sequence from medical device use, and cannot be reasonably explained by known characteristics of the subject's clinical data.
- Possibly related: follows a reasonable temporal sequence from medical device use, but could have been produced by the subject's clinical state regardless of the medical device.
- Probably not related: temporal association is such that the medical device use is not likely to have had any reasonable association with the observed event.
- Not related: no relationship to the use of the medical device is perceived.

Abnormalities of vital signs and laboratory results are to be recorded as AEs only if they are considered by the Investigator as clinically significant (symptomatic, requiring corrective treatment, leading to discontinuation, or fulfilling a seriousness criteria).

Any pre-existing conditions or signs and/or symptoms present in a subject prior to the Screening Visit should be recorded as medical/surgical history.

In this study, the following events will be reported to the authorities on expedited basis:

- All SAEs (including SADEs) will be expeditiously reported to the relevant European Regulatory Authorities and the Ethics Committees.
- All newly discovered pregnancies will be expeditiously reported, if required by the local regulations.
- All suspected USADEs will be expeditiously reported to the US Food and Drug Administration (FDA) and the US Institutional Review Boards.
- All incidents occurring in Canada will be expeditiously reported to Health Canada.

All device deficiencies are to be recorded in the appropriate electronic CRF.

### **13.1.4 Anticipated Adverse Device Effects**

The ADEs anticipated with the administration of Gelesis100 in overweight or obese subjects include nausea, dyspepsia (heartburn), abdominal distension (bloating), flatulence, abdominal pain, diarrhea, defecation urgency, and constipation. These AEs

---

were observed in the FLOW study. A comprehensive list of anticipated ADEs is provided in the Investigator's Brochure (8).

### **13.1.5 Risk Analysis**

The Sponsor has established and maintains a process for identifying hazards associated with the use of its products, estimating, evaluating, controlling these risks and monitoring the effectiveness of the control. Detailed information regarding risk analysis is available in the Investigator's Brochure (8).

### **13.1.6 Precautions to Minimize Risk**

To minimize technical and medical complications, the investigational medical device should be used only as instructed in the Clinical Investigation Plan. This includes:

- administering the prescribed amount of medical device before lunch and dinner (3 capsules)
- drinking the prescribed volume of water (approximately 100 mL + 500 mL) at the prescribed timing before meal
- consuming food at the prescribed timing (20 to 30 min after medical device administration)

## **13.2 Pregnancy**

In case of pregnancy, the investigational medical device use must be discontinued and the Sponsor informed. Every effort should be made to follow up the pregnancy until its outcome is available.

The Contract Research Organization (CRO) Clinical Safety will provide the Investigator with the Pregnancy Reporting Form for completion. If the pregnancy is to be terminated, the anticipated date of termination should be provided.

## **13.3 Responsibilities for Adverse Event and Pregnancy Reporting**

### **13.3.1 Responsibilities of the Investigator**

- to inform the Sponsor about all AEs
- to inform the Sponsor about all SAEs, newly discovered pregnancies or pregnancy outcomes, within 24 h of awareness of the events, by:
  - entering the information about the event into the electronic CRF
  - in case the Investigator does not receive an automatic notification from the electronic CRF system of successful SAE submission or electronic CRF data entering is not possible:
    - printing the completed section of the electronic CRF (or in case completion of electronic CRF is not possible, completion of paper SAE form)
    - signing the completed SAE form

---

- sending the scanned SAE form by e-mail to the CRO Clinical Safety at [[contact]](mailto:[contact]) (or in case sending a scan is not possible, faxing it to the CRO Clinical Safety at [contact])
- to inform the Sponsor about all device deficiencies
- to make every effort to follow up the subject to a satisfactory resolution of the safety event or until the end of the study
- to respond to follow-up requests from the Sponsor/CRO Clinical Safety

### **13.3.2 Responsibilities of the Sponsor**

- to ensure that:
  - all AEs are recorded and reviewed with the Investigators
  - all SAEs are reported to the relevant European Regulatory Authorities/Ethics Committees as required by the local regulations
  - all newly discovered pregnancies are reported as required by the local regulations
  - all suspected USADEs are reported to the FDA/Institutional Review Boards as required by the US regulations
  - all SADEs/incidents are reported to Health Canada as required by the Canadian regulations
  - all device deficiencies are recorded and reviewed with the Investigators
- during the course of the study, inform in writing all Investigators about all SAEs occurring at any of the participating sites
- to collect and maintain records of all AEs, device deficiencies, and pregnancies

## **14. TREATMENT/STUDY DISCONTINUATION**

### **14.1 Temporary Treatment Discontinuation**

The subjects may discontinue the study treatment for a period not exceeding 3 days for a valid medical reason, at the discretion of the Investigator.

### **14.2 Permanent Treatment/Study Discontinuation**

#### **14.2.1 Reasons**

The subject may withdraw from the treatment with the investigational product (and the study) at any time and irrespective of the reason.

The Investigator will discontinue the investigational product (and the study) for the following reasons (after assessing their clinical relevance):

- contraception cessation
- pregnancy or wish of pregnancy
- significant intolerance to the study product
- an increase of  $\geq 0.5\%$  point ( $\geq 5.5$  mmol/mol) in HbA1c from Baseline Visit in subjects with treated or untreated type 2 diabetes, or any increase if the new value falls in the

Property of Gelesis, Srl. – Strictly Confidential

---

range of the exclusion criteria for HbA1c (see Section 8.4) after confirmation following a re-check at the next study visit (or before)

- an increase of  $\geq 10\%$  in total cholesterol, LDL cholesterol, or triglycerides from Baseline Visit in subjects with elevated lipids at Baseline Visit, or any increase if the new values fall in the range of the exclusion criteria for lipids (see Section 8.4) after confirmation following a re-check at the next study visit (or before)
- an increase of  $\geq 10$  mm Hg in supine SBP and/or supine DBP from Baseline Visit in subjects with treated or untreated hypertension, or any increase if the new values fall in the range of the exclusion criteria for blood pressure (see Section 8.4) after confirmation following a re-check at the next study visit (or before), based on the mean of two consecutive readings
- poor subject compliance with the study procedures and recommendations and/or major protocol deviation
- it is the best interest of the subject (including the need to add prohibited medications)

The subject is withdrawn from the treatment and the study if the treatment arm is unblinded for emergency reasons (see Section 15.5.4.2) or for a reason other than the interim analysis before the end of the treatment.

#### **14.2.2 Procedures**

When confirmed, a permanent treatment/study discontinuation should be recorded by the Investigator in the appropriate electronic CRF and, if applicable, reported to the relevant Ethics Committee/Institutional Review Board.

Every effort should be made to complete the clinical and laboratory evaluations required for Visits 12 and 13 as soon as possible (combined assessments).

Subjects who have withdrawn from the treatment/study cannot be re-enrolled in the study. Their screening number and randomization number must not be re-used.

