#### **10.1.4 Post-Treatment Follow-up Period**

The duration of the follow-up period is 28 days with a visit window of 3 days for Visit 14 but no visit window for Visit 13 (see Section 12.1).

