## **11. STUDY ENDPOINTS**

When hydrated, Gelesis100 has some weight by itself. At any time following the first day of Gelesis100 administration, subjects may accumulate up to 1 kg of hydrated Gelesis100 in their gastrointestinal tract. Therefore, it is likely to observe an initial weight gain during the first days or weeks of treatment until the extra weight is counter-balanced by the weight loss caused by Gelesis100. An interval of 2 days is required for any remaining Gelesis100 to be eliminated from the gastrointestinal tract. For these reasons, to ensure that the weight of Gelesis100 does not mask the true amount of weight loss, the end of treatment assessment of body weight and weight-related parameters will be performed on Day 171, approximately 60 h after the last administration of Gelesis100.

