## **11.3 Assessment Methods**

All the assessments, unless otherwise specified, will be performed in the morning (between approximately 7 am and 10 am), before product intake, on fasting subjects (10 to 12-h fast) with no moderate or intense physical activity within the past 12 h. Physical examination, dietary interview, and electrocardiogram (ECG) can be performed at any time during the day regardless of food or investigational product intake.

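### Section 14.2.2 sets no minimum time off product before the early-termination weight, so some Gelesis100 subjects can be weighed without the 2-day interval that Section 11 calls required

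*Combined protocol and SAP*

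**What the plan says.** Section 11 explains why the final weight is taken late. Any time after the first dosing day, "subjects may accumulate up to 1 kg of hydrated Gelesis100 in their gastrointestinal tract". It continues: "An interval of 2 days is required for any remaining Gelesis100 to be eliminated from the gastrointestinal tract". The end-of-treatment weight is therefore set on Day 171, "approximately 60 h after the last administration of Gelesis100".

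For completers the schedule enforces this. Dosing ends on Day 168 (Section 2, footnote H). Section 12.1 says that Visit 13 "should occur 2 days after Visit 12", and Section 10.1.4 gives a 3-day window for Visit 14 "but no visit window for Visit 13".

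For subjects who discontinue, Section 14.2.2 says: "Every effort should be made to complete the clinical and laboratory evaluations required for Visits 12 and 13 as soon as possible (combined assessments". No minimum time since the last intake is given there, and no other section supplies one. Under Section 11.3, assessments "will be performed in the morning (between approximately 7 am and 10 am), before product intake".

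The co-primary endpoints are percent change in weight, and at least 5% weight loss, from baseline to Day 171 (Section 11.1.1). Section 15.2 lists Day 171 without a window. Section 15.7.3 imputes missing points by multiple imputation and leaves the detail to a separate SAP, which is not part of the document.

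**The concern.** The protocol calls the interval necessary for a valid end-of-treatment weight, then prescribes a combined visit that can omit it. The case is foreseeable. Section 14.2.1 ties several discontinuations (HbA1c, lipids, blood pressure) to a re-check at the next study visit or before, so a subject may be on site and still taking product when the decision is made.

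Retained gel adds weight only in the Gelesis100 arm, so randomization does not cancel the error. A weight collected under Visit 13 procedures could be entered as Visit 13 and analysed as Day 171. That would shrink the arm difference, which is tested against a 3.0-point margin (Section 15.4). It would also lower the active responder rate, which Section 6.1 judges against a fixed 35%.

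**Working it through.** **1. Time since last dose.** Assume the dinner dose is taken at about 7 pm.

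| Weight | Last dose | Weighed | Gap |
|---|---|---|---|
| Completer, Visit 13 | Day 168, 7 pm | Day 171, 7 to 10 am | 60 to 63 h |
| Subject stopped and weighed at one morning visit | previous evening, 7 pm | 7 to 10 am | 12 to 15 h |

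The first row reproduces Section 11's figure of about 60 h. The second falls well short of 2 days.

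**2. Error per affected subject** = retained kg × 100 / body weight. The documents give no mean weight for this trial, so 80 to 120 kg is assumed. Section 8.3 recommends that at least 92% of subjects weigh under 120 kg. The upper value of 1 kg is Section 11's. A lower case keeps only the previous day's two doses: 2 × about 225 mL (Section 9.1.1), about 0.45 kg.

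| Retained | 80 kg | 100 kg | 120 kg |
|---|---|---|---|
| 1 kg | 1.25 points | 1.00 | 0.83 |
| 0.45 kg | 0.56 | 0.45 | 0.38 |

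**3. Dilution of the arm difference if these weights are used as Day 171 values** = dropout × share affected × error. Dropout is 30% (Section 15.4). The share affected is not in the documents. At 100 kg:
- all affected, 1 kg: 0.30 × 1 × 1.00 = 0.30 points (0.375 at 80 kg, 0.25 at 120 kg)
- half affected, 1 kg: 0.30 × 0.5 × 1.00 = 0.15
- half affected, 0.45 kg: 0.30 × 0.5 × 0.45 = 0.07
- all affected, 1 kg, at the 5% dropout seen with this dose in the 12-week FLOW study (Section 5.2.1.2): 0.05 × 1 × 1.00 = 0.05

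**4. Active responder rate under the same use.** A responder is lost when true loss lies between 5 and 5 + error. Assume normal losses with SD 5.1 (FLOW, 2.25 g arm) and a mean loss of 3.0, 4.5 or 6.1.
- Error 1.00: probability 0.069, 0.077, 0.078. Times 0.30 this is 2.1 to 2.3 points; times 0.15, 1.0 to 1.2; times 0.05, at most 0.4.
- Error 0.45: probability 0.032 to 0.035. Times 0.15 this is about 0.5 points.

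**5. Power.** The plan's figure reproduces: 161 per arm, 4.5 − 3.0 = 1.5, SD 5.0, one-sided 0.05 gives 85.2% against the stated 85%. If dropouts' weights are analysed, the matching size is 230 per arm, where power without retained gel is 94.2%. At 100 kg it becomes 82.4% with 0.30 points of dilution and 89.4% with 0.15.

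**6. If Day 171 is missing and imputed.** The simulation used 1,500 trials of 230 per arm, 30% random dropout, true difference 4.5 and SD 5. It added 1.0 point to every on-product active weight and ran 10 imputations within arm. The correlation between the last on-product change and the Day 171 change was assumed to be 0.70, 0.85 or 0.95. The simulation standard error is 0.012 to 0.013.

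| Handling | Mean difference at 0.70 / 0.85 / 0.95 |
|---|---|
| No retained gel | 4.52 / 4.49 / 4.53 |
| Early weight used as Day 171 | 4.21 / 4.18 / 4.22 |
| Imputed within arm from on-product weight | 4.51 / 4.53 / 4.51 |

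**7. The opposite mistake.** If an early terminator's washed-out weight is used as though it were on-product, the imputation removes gel that is no longer there. With all active dropouts washed out, the shift is 0.30 × 1.00 × slope. With equal SDs the slope equals the correlation, so at 0.70 to 0.95 the difference becomes 4.71 to 4.79. A separate check gave about 4.74. This error favours the product.

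**The case against.** The best defence is that Section 11 ties the interval to the Day 171 weight. All weights at Visits 3 to 12 are taken during treatment without washout, and Visit 12 itself follows the last Day 168 dose by roughly the same 12 to 15 h. An early-termination weight can be seen as one more such weight. Day 171 has no window and missing points are imputed, so the natural reading is that an early terminator's Day 171 weight is missing. Completers are weighed both on product and after washout, two days apart, so within-arm imputation can learn the shift. Step 6 shows that it does. All of this stands, and it limits the consequence. What it does not answer is that Section 14.2.2 collects this weight as part of Visit 13, and the protocol does not say how it is classified.

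A reader might infer three stronger things that the documents do not support:
- *That every early terminator loses the washout.* Section 14.2.2 is silent on time since last dose; it does not forbid an interval. Late visits are 28 days apart and subjects may withdraw at any time, so some will already have been off product for 2 days. Others will not attend at all.
- *That planned power falls from 85% to about 69%.* That applies dropouts' error to the 161 per arm, who are completers and all get the interval. The coherent comparison is at 230 per arm, in step 5.
- *That the missing interval could produce a false claim of effect.* An on-product weight used as Day 171 works against Gelesis100 and does not inflate type I error.

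**Conclusion.** The point holds as a minor one. Section 14.2.2 permits a Visit 13 weight without the interval that Section 11 calls required, and no other section restores it. The error is up to 1 kg per affected subject, in the active arm only.

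The effect on the co-primary results depends on a classification rule left to the SAP. The ceiling of about 0.30 points and about 2 responder points needs 30% dropout, every active dropout weighed on product, the full 1 kg in each, a weight of 100 kg, and use as Day 171 values. With half affected, the dilution is 0.07 to 0.15 points. With within-arm imputation from on-product weights there is no detectable shift, although that simulation assumed random dropout. Confidence is medium, because the share affected and the SAP rule are unknown.

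**What to change.** In Section 14.2.2, keep the safety and laboratory evaluations prompt. Take the early-termination weight and weight-related measures at least 2 days (about 60 h) after the last intake where the subject can attend then. Otherwise take a same-day weight and flag it as on-product. Record the time of last intake; dates of administration are already source data (Appendix 5).

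In the SAP, state that a weight taken before the interval has elapsed is never a Day 171 value, that Day 171 is imputed within treatment arm, and that washed-out and on-product early-termination weights are not pooled as one imputation predictor. The last rule must accompany the timing change, or the timing change can introduce the upward shift in step 7.

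The cost is a delayed or extra short visit for some early terminators, one CRF field, and short additions to Section 14.2.2 and the SAP. Some subjects will not return, and their flagged same-day weight will be the only one available.
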